We have carefully considered but decided against proposing a prospective cohort study of the predictive accuracy of risk assessment tools because this design would have an insurmountable flaw if undertaken alongside current NHS practice. The fundamental aim of risk assessment is to predict patients whose VTE will be prevented by prophylaxis. Over 70% of medical patients in the UK receive prophylaxis when the Department of Health risk assessment tool has been used (NICE 2018). In this situation, around half of the VTE that could have been prevented by prophylaxis will have been prevented and the prognostic model will largely be predicting VTE that were not prevented by currently-used prophylaxis. Any prognostic model derived in this setting would therefore be based on factors that predict non-preventable VTE whilst under-estimating (or missing) those that predict preventable VTE. A risk assessment tool that predicted non-preventable VTE while failing to predict preventable VTE would potentially be worse than useless.

In accordance with the commissioning brief, we propose and provide justification for an alternative efficient study design to estimate the cost-effectiveness of VTE risk assessment tools for hospital inpatients. We will use decision-analysis modelling of published evidence to determine how the cost-effectiveness of prophylaxis varies for different thresholds of risk.

This will determine whether risk assessment has the potential to be cost-effective compared with prophylaxis for all and, if so, what threshold of risk should be used for providing prophylaxis and what trade-off between sensitivity and specificity would be optimal for a risk assessment tool. We used this approach in our evaluation of risk assessment tools for prophylaxis for people with lower limb immobilisation due to injury (HTA15/187/06), showing that a risk assessment tool with sensitivity around 90% and specificity around 50% would be optimal, assuming an appropriate trade-off on the receiver operating characteristic (ROC) curve.

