We undertook a scoping search of VTE risk assessment tools from inception to May 2018 by adapting the search strategy we used in our systematic review of risk assessment tools in lower limb immobilisation (Pandor 2018). This identified 5662 potentially relevant citations. Initial screening identified recent systematic reviews of VTE risk assessment models (RAMs) in acutely ill medical patients (Stuck 2017) and hospitalised non-surgical patients (Huang 2013), along with nine recent relevant primary studies not included in these reviews (Grant 2016, Liu 2016, Rafizadeh 2016, Greene 2016, Elias 2017, de Bastos 2016, Blondon 2018, Zhou 2018, Depietri 2018, Hostler 2018). We also examined the review of RAMs undertaken for NICE guidance (NICE 2018).

Stuck et al identified 11 studies reporting eight RAMs: the 4-Element RAM, Caprini RAM, Woller full logistic model, Geneva risk score, IMPROVE tool, Kucher score, Rothberg multivariable model and Padua Prediction Score. Huang et al identified 11 studies reporting RAMs, six derived from primary data and five based on expert opinion. The NICE review identified 22 studies evaluating 13 RAMs, including the Caprini RAM, Kucher score, Geneva risk score, IMPROVE tool, Intermountain RAM, Khorana Score, Padua Prediction Score and Trauma Embolic Scoring System.

There was substantial variation between the primary studies in terms of populations, methods and outcomes used, which precluded meta-analysis and limited comparisons

between RAMs. Overall, the studies suggested that the RAMs had modest prognostic value with most reporting c-statistics around 0.6 to 0.7. Sensitivity and specificity depended upon the threshold used but high sensitivity could only be achieved by substantial loss of specificity. An ideal RAM could not be recommended by any of the reviews but this does not mean that risk assessment has no value. Risk assessment based on modest prognostic accuracy could still be useful, as any targeting of prophylaxis may be an improvement on untargeted treatment.

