We will use existing literature to estimate the risks of VTE and bleeding outcomes (as defined above) for the cohort if no prophylaxis is given and then use relative risk estimates from existing systematic reviews of VTE prophylaxis for relevant inpatient populations to estimate the VTE and bleeding risks with prophylaxis (NICE 2018, Kahn 2018). Alternatively, if more reliable event rate estimates are available for inpatients receiving prophylaxis, we will use the inverse of the relative risks to estimate the risks in those not receiving prophylaxis. We will explore using different risk estimates for different inpatient populations, depending upon the data available.

The proportion of patients having VTE prophylaxis for each strategy is determined by the risk of VTE in the population and the sensitivity and specificity of the strategy for identifying patients who go on to have VTE. The proportion having VTE and / or bleeding events is then calculated for those receiving or not receiving prophylaxis which is dependent on the factors above plus the effectiveness and safety of prophylaxis. In the secondary analysis the risk of bleeding events will also depend upon the sensitivity and specificity of the IMPROVE bleeding risk score for predicting bleeding events.

The sensitivity and specificity of each risk-assessment tool for predicting VTE will be estimated using data from the systematic review, with the clinical expert group being used to judge the appropriateness of estimates and select between studies if more than one estimate exists for any tool.

We will also undertake the following threshold analyses:

- 1. Theoretical risk-assessment tools will be examined with sensitivity and specificity varying across a credible ROC curve, to determine the balance of sensitivity and specificity at which effectiveness (QALYs) and cost-effectiveness (net benefit assuming willingness to pay £20,000/QALY or £30,000/QALY) is optimised
- 2. A one-way sensitivity analysis will vary the baseline risk of VTE in a comparison between prophylaxis for all and prophylaxis for none, to determine the thresholds of baseline risk at which prophylaxis for all is more effective and cost-effective than prophylaxis for none (i.e. the threshold at which the benefits of prophylaxis outweigh the risks and the threshold at which the benefits outweigh the risks and costs)

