We will use the decision-analysis model to (1) explore the potential impact of uncertainty in estimates of predictive accuracy, (2) identify the optimal balance of sensitivity and specificity for a risk-assessment tool, and (3) identify the appropriate risk threshold for providing prophylaxis. The first objective can be undertaken with limited data and the latter two by using theoretical risk-assessment tools with varying prognostic performance. These analyses will help to inform discussions reported in the NICE guideline as to whether 70% of inpatients receiving prophylaxis according to the Department of Health tool or the estimated 40% with the IMPROVE tool is more appropriate. We will also be able to determine which existing risk-assessment tools appear to operate at thresholds for performance likely to be optimal according to our model and, for risk-assessment scores, which score appears to provide an optimal threshold.

The model can therefore provide evidence to indicate whether more liberal or restrictive use of prophylaxis is likely to be appropriate. Ultimately, however, primary research will be required to determine the impact of a risk-adjustment tool (or tools) in practice, hence our concurrent plan to determine the feasibility of efficient methods to evaluate alternative approaches to the use of VTE prophylaxis.

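### Threshold analysis 1 seeks the optimal sensitivity/specificity balance on a single ROC curve, although existing tools span c-statistics of about 0.6 to 0.7 and the optimal pair depends strongly on the curve

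*Protocol*

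**What the plan says.** Protocol section 4.2 (Decision analysis modelling) lists two threshold analyses. The first reads "Theoretical risk-assessment tools will be examined with sensitivity and specificity varying across a credible ROC curve", and its purpose is "to determine the balance of sensitivity and specificity at which effectiveness (QALYs) and cost-effectiveness" are optimised. The curve is in the singular, and neither its shape nor its area is given. The second varies baseline VTE risk in a comparison of prophylaxis for all with prophylaxis for none, and uses no ROC curve.

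Section 16.1 (Evidence synthesis) says how such results will be used. The team will establish "which existing risk-assessment tools appear to operate at thresholds for performance likely to be optimal according to our model" and, for scores, "which score appears to provide an optimal threshold". It adds that these analyses will inform whether about 70% of inpatients treated (Department of Health tool) or about 40% (IMPROVE tool) is more appropriate.

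Section 1.0 (Introduction) gives two relevant facts. Under Existing literature, the primary studies are summarised as "most reporting c-statistics around 0.6 to 0.7". Under Background and Rationale, the team's earlier lower-limb model is reported to have found that "a risk assessment tool with sensitivity around 90% and specificity around 50% would be optimal", with the condition "assuming an appropriate trade-off on the receiver operating characteristic (ROC) curve".

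**The concern.** For fixed benefits, harms and mean risk, net benefit is greatest where the slope of the ROC curve equals the odds at the risk threshold divided by the odds of the mean risk. That slope, which is the likelihood ratio at the cut-off, is the same for every tool. The sensitivity/specificity pair at which it is reached is not the same. It moves with the tool's discrimination.

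A balance read from one curve therefore describes tools on that curve only. The protocol expects existing tools to lie on several. If the single pair became the yardstick, a weaker tool's cut-off could be praised or criticised by a standard that does not fit it. The treated share reported as optimal would also reflect the choice of curve as well as the benefits and harms.

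**Working it through.** **1. The protocol's own operating point.** The 90%/50% optimum of the earlier model cannot be re-derived, because its curve, costs, utilities and VTE risk are not in the protocol. What it implies about discrimination can be checked.
- Any concave ROC curve through sensitivity 0.90 and specificity 0.50 has an area of at least (0.90 + 0.50)/2 = 0.70.
- On an equal-variance binormal curve, d = z(0.90) + z(0.50) = 1.282, and the area is Φ(1.282/√2) = 0.818.
- On binormal curves at 90% sensitivity, specificity is 17.8% (c = 0.60), 23.1% (0.65) and 29.5% (0.70).

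So a pair that is optimal on one credible curve can be out of reach for tools in the range that section 1.0 reports.

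**2. How the optimum moves.** Inputs: c from 0.60 to 0.70 (section 1.0). Assumed: equal-variance binormal curves, likelihood ratio (LR) 0.5 at the cut-off, mean risk p = 1%. Formulas: d = √2·z(c); x = (ln LR + d²/2)/d; sensitivity = Φ(d − x); specificity = Φ(x); treated = p·sens + (1 − p)(1 − spec).

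For c = 0.60: d = 0.358; x = (−0.693 + 0.064)/0.358 = −1.76; sensitivity = Φ(2.11) = 98%; specificity = Φ(−1.76) = 4%; treated = 0.01 × 0.983 + 0.99 × 0.960 = 96%.

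| c | Sensitivity | Specificity | Treated |
|---|---|---|---|
| 0.60 | 98% | 4% | 96% |
| 0.65 | 94% | 16% | 84% |
| 0.70 | 90% | 29% | 72% |
| 0.82 | 88% | 54% | 46% |

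The result does not hang on LR = 0.5. With the slope implied by 90%/50% on its own binormal curve, exp(−1.282²/2) = 0.440, the optima are 99.3%/1.7% at c = 0.60, 96.2%/10.9% at 0.65 and 93.0%/23.1% at 0.70.

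**3. What is lost if the c = 0.70 optimum is carried to a weaker tool.** Value per patient = B·p·sens − C·treated, with an assumed gain B = £3,000 per VTE patient treated and an assumed harm plus cost C per patient treated. The optimal LR is C(1 − p)/[(B − C)p]; for C = £15 and p = 1% it is 0.497, in line with step 2. The tool is held either to the sensitivity or to the specificity of the c = 0.70 optimum.

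| Tool c | p | C | For all | Own optimum | Sensitivity held | Specificity held |
|---|---|---|---|---|---|---|
| 0.60 | 1% | £15 | £15.00 | £15.07 | £14.69 | £13.93 |
| 0.65 | 1% | £15 | £15.00 | £15.53 | £15.46 | £15.26 |
| 0.60 | 1% | £20 | £10.00 | £10.54 | £10.36 | £9.69 |
| 0.60 | 1% | £25 | £5.00 | £6.87 | £6.86 | £6.48 |
| 0.60 | 0.5% | £15 | £0 | £2.12 | £2.08 | £2.08 |
| 0.60 | 2% | £15 | £45.00 | £45.00 | £44.71 | £44.14 |

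The first two rows take the c = 0.70 pair at LR 0.5, and the others at the exact LR.

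A second illustration uses the 1.0% risk threshold of the US model cited in section 1.0 and an assumed mean risk of 2%. In net true positives per 10,000, a c = 0.60 tool scores 101.5 at its own optimum and prophylaxis for all scores 101.0. The tool held to the c = 0.70 optimum scores 99.0 (sensitivity held) or 94.0 (specificity held). For a c = 0.65 tool the figures are 104.5 at its own optimum, and 104.0 or 102.7.

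**The case against.** A reader might infer that the protocol will apply the single-curve pair to tools on other curves and so call the wrong cut-offs optimal. The document does not support that.
- Section 16.1 speaks of optimality according to the model, not according to the pair from threshold analysis 1.
- Section 4.2 enters each selected tool at its own sensitivity and specificity in a fully incremental analysis that includes prophylaxis for all. A modelled tool that does worse than treating everyone would be seen to do so.
- Threshold analysis 2 gives a risk threshold that needs no curve.
- Section 16.1 refers to theoretical tools of varying prognostic performance and to exploring uncertainty in predictive accuracy. Both may already mean several curves.

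A reader might also take the optimal balance to be a main output. Section 8.0 lists an optimal strategy, risk thresholds, value of information and an implementation-study proposal, but no sensitivity/specificity pair. Nor is 90%/50% proposed as a target for inpatients. It comes from another population and carries its own condition.

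These points stand, and so does the observation that the losses in the working are often pennies. What remains is that section 4.2, which defines the analysis, names one curve and one balance as its target. Section 16.1 does not say that tools and score cut-offs will be judged by anything other than that balance.

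**Conclusion.** The point holds as a minor one. Threshold analysis 1 as written gives an answer specific to one unspecified curve. Within the protocol's own range of c-statistics, the optimal specificity moves from about 4% to 29% and the optimal treated share from 96% to 72%, with the benefits and harms unchanged. That matters for the planned comment on 70% versus 40% treated.

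The consequence is conditional. If remarks on tools and cut-offs rest on the single pair, the loss ranges from negligible (a c = 0.65 tool at £15.46 against £15.53) to enough to fall below prophylaxis for all (a c = 0.60 tool at £14.69 against £15.00). The main cost-effectiveness comparison is untouched.

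The sizes rest on equal-variance binormal curves, linear net benefit, and assumed values for mean risk, gain and harm. None of these values is given in the protocol. The dependence of the pair on the curve does not rest on those particular values.

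**What to change.** In section 4.2, replace the single curve with a family of credible ROC curves spanning the c-statistics found in the review, for example 0.60, 0.65 and 0.70. Report the optimal balance and the treated share for each curve. In section 16.1, state that each existing tool or score cut-off will be judged by net benefit at its own ROC points, or by the risk threshold from threshold analysis 2, and not by closeness to one sensitivity/specificity pair. If several curves were always intended, the same wording makes that plain.

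The cost is a few more model runs and a short change of text. No data collection changes.

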2.0 Aims and objectives

We aim to evaluate the cost-effectiveness of VTE risk assessment tools in hospital inpatients, determine the optimal approach to providing VTE prophylaxis and determine how changing the risk threshold for prophylaxis affects cost-effectiveness. Our specific objectives are to:

- 1. Update recent systematic reviews (Huang 2013, Stuck 2017, NICE 2018) to identify tools for VTE risk assessment in hospital inpatients and estimate prognostic accuracy
- Undertake decision-analysis modelling to determine the cost-effectiveness of VTE risk assessment compared to prophylaxis for all and prophylaxis for none, specifically determining the risk threshold that optimises effectiveness (QALYs) and costeffectiveness (i.e. maximises net benefit assuming willingness to pay according to NICE thresholds)
- 3. Use the decision-analysis model to identify key areas of uncertainty and determine the value of gathering additional information to reduce uncertainty
- 4. Pilot the use of efficient methods alongside routine practice to determine the feasibility of a future implementation study of VTE risk assessment tools in hospital inpatients

The PICO terms for the main research question are:

Population:	NHS hospital inpatients

- Intervention: VTE prophylaxis (pharmacological or mechanical) based on a risk assessment tool
- Comparator: VTE prophylaxis for all patients or none
- Outcomes: VTE and bleeding events, QALYs, incremental cost per QALY gained, incremental net monetary benefit

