At the end of phase 1 of the model each patient will be characterised according to whether or not they have suffered VTE or bleeding events. They will then enter phase 2 of the model, which will determine the lifetime costs and QALYs accrued by each patient. This phase will incorporate any long term consequences of both VTE and major bleeds.

Each patient in the cohort will accrue costs and outcomes determined by whether they receive prophylaxis or not, whether they developed clinically significant VTE, and whether they suffer any bleeding events. We will use parameter estimates and a model structure developed for our recent study of the cost-effectiveness of VTE prophylaxis for lower limb immobilisation due to injury (HTA15/187/06).

The total costs and QALYs accrued across the cohort will be calculated and a fully incremental analysis will be undertaken. Costs will be evaluated from an NHS and personal social services perspective. Future costs and benefits will be discounted at 3.5% in line with current best practice, as defined by NICE (NICE 2013).

Uncertainty about parameters that are subjected to formal evidence synthesis will be characterised by drawing samples from their appropriate joint posterior distributions. For parameters where the studies yield no or minimal relevant information with which to populate the model, elicitation sessions with experts, and scenario analyses will be considered. These sources of evidence will be combined to produce estimates of model parameters and define the associated probability distributions.

Differences in resource use between the different VTE prophylaxis strategies, including medications, clinical time to implement risk assessment, and management of VTE and bleeding-related adverse events, will be valued by applying Department of Health reference costs (Department of Health 2014) or PSSRU unit costs (Curtis 2015) for episodes of care and BNF list prices for medications (British National Formulary 2016).

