Analyses will be undertaken to identify the key parameters determining the costeffectiveness of the different strategies with the objective of identifying how secure the conclusions of the economic analyses are, given the available evidence. Uncertainty with respect to model parameters will be explored with a probabilistic sensitivity analysis (PSA). The information derived from PSA will be summarised graphically (within a costeffectiveness acceptability curve). The probability that the cost-effectiveness of the intervention is within the £20,000-£30,000 per QALY range, reflecting the thresholds typically used by NICE (NICE, 2013) in appraising health technologies will be explicitly reported.

If there is evidence that the tools perform differently in different subgroups, then we would explore this in the economic model to determine whether these differences translated into different estimates of cost-effectiveness.

The decision analytic model will be used to estimate the value of information of further primary research and determine the optimal direction of future research, whilst taking into account restrictions placed on potential research by widespread use of VTE prophylaxis. The

expected value of partial perfect information (EVPPI) will be estimated for groups of parameters. This will be done using the Sheffield Accelerated Value of Information application which calculates EVPPI directly from the PSA results avoiding the need for computationally expensive nested double loop simulations (Strong 2014). If the EVPPI estimates suggest that further primary research may be valuable to reduce the uncertainty around specific groups of parameters, then expected value of sample information (EVSI) analysis will be performed to inform decisions regarding future primary research (Strong 2015).

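### The one PSA probability singled out for explicit reporting treats £20,000 and £30,000 per QALY as a target band, so as worded it cannot separate good value from poor value

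*Protocol*

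**What the plan says.** All of this is in the Protocol.

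- Section 4.2, on the PSA, first plans a graph: "The information derived from PSA will be summarised graphically (within a costeffectiveness acceptability curve").
- The next sentence names one number: "The probability that the cost-effectiveness of the intervention is within the £20,000-£30,000 per QALY range". It goes on: "reflecting the thresholds typically used by NICE (NICE, 2013) in appraising health technologies will be explicitly reported".
- Earlier in section 4.2, the threshold analysis of theoretical tools looks for the point where "cost-effectiveness (net benefit assuming willingness to pay £20,000/QALY or £30,000/QALY) is optimised".
- Section 2.0 (Aims and objectives) sets the criterion for the optimal risk threshold as the one that "maximises net benefit assuming willingness to pay according to NICE thresholds". Section 3.1 repeats this, and the PICO list in 2.0 includes incremental net monetary benefit as an outcome.
- Section 4.2 compares prophylaxis for all, prophylaxis for none and several risk-assessment tools, and says that "a fully incremental analysis will be undertaken".

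**The concern.** A willingness-to-pay threshold is a ceiling: a strategy is acceptable if its cost per QALY gained falls below it, and a lower cost is better. The PSA sentence asks instead how often the cost per QALY falls between two ceilings. That excludes the most favourable results (cost-saving, or cheap per QALY) together with the least favourable.

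The work is meant to inform NICE guidance (section 8.0). A reader who sees a probability of 1% beside the NICE thresholds would take the strategy to be poor value, when the same PSA draws could show it to be almost certainly good value. An analyst who follows the sentence as written would produce that number.

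**Working it through.** **The plan's own figure.** There is none to reproduce. The protocol gives no PSA result and no PSA parameters, so every input below is an assumption, chosen only to show how the statistic behaves.

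**Formulae.** Let dC and dQ be the incremental cost and QALYs of one strategy against one comparator, independent and normal, with means mC, mQ and standard deviations sC, sQ. At threshold L:

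P(cost-effective at L) = P(L·dQ − dC > 0) = Φ[(L·mQ − mC) / √(L²·sQ² + sC²)]

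When dQ > 0, net benefit is positive exactly when dC/dQ < L. If negative dQ is rare, then:

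P(£20,000 ≤ dC/dQ ≤ £30,000) ≈ P(cost-effective at £30,000) − P(cost-effective at £20,000)

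So the in-range probability is the *rise* of a two-strategy acceptability curve between the two thresholds. The decision needs its *height* at each.

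**First set of assumed inputs (mQ = 0.005).**

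- Case A: mC = £20, sC = £20, sQ = 0.0015; mean ICER £4,000.
  - At £20,000: (100 − 20)/√(30² + 20²) = 80/36.06 = 2.22, giving 0.987.
  - At £30,000: (150 − 20)/√(45² + 20²) = 130/49.24 = 2.64, giving 0.996.
- Case B: mC = £50, sC = £30, sQ = 0.002; mean ICER £10,000.
  - At £20,000: (100 − 50)/√(40² + 30²) = 50/50 = 1.00, giving 0.841.
  - At £30,000: (150 − 50)/√(60² + 30²) = 100/67.08 = 1.49, giving 0.932.
- Case C: mC = £100, sC = £30, sQ = 0.002; mean ICER £20,000.
  - At £20,000: (100 − 100)/50 = 0, giving 0.500.
  - At £30,000: (150 − 100)/67.08 = 0.745, giving 0.772.

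| Case | Mean ICER | P(cost-effective at £20,000) | P(cost-effective at £30,000) | P(in range) |
|---|---|---|---|---|
| A | £4,000 | 0.987 | 0.996 | 0.009 |
| B | £10,000 | 0.841 | 0.932 | 0.091 |
| C | £20,000 | 0.500 | 0.772 | 0.272 |

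Value for money falls from A to C while the in-range probability rises. Simulation with a million draws gives the same in-range values.

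**Second set (mQ = 0.01; same coefficient of variation, CV, for cost and QALYs; cost SD at least £20; one million draws).**

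| Mean ICER | CV | P(cost-effective at £20,000) | P(cost-effective at £30,000) | P(in range) |
|---|---|---|---|---|
| £5,000 | 0.2 | 1.000 | 1.000 | 0.000 |
| £5,000 | 0.5 | 0.928 | 0.950 | 0.023 |
| £10,000 | 0.2 | 0.987 | 0.999 | 0.012 |
| £10,000 | 0.5 | 0.815 | 0.897 | 0.082 |
| £25,000 | 0.2 | 0.218 | 0.740 | 0.522 |
| £25,000 | 0.5 | 0.378 | 0.602 | 0.224 |
| £60,000 | 0.2 | 0.001 | 0.013 | 0.012 |
| £60,000 | 0.5 | 0.103 | 0.185 | 0.082 |

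A cost-saving strategy (mean saving £50, SD £20; QALY CV 0.3) has a probability above 0.999 of being cost-effective at either threshold and below 0.0001 of being in range.

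The £10,000 and £60,000 rows are decisive. At each CV the two strategies get the same in-range probability, although one is probably good value and the other probably is not. Of the mean ICERs tried, the statistic is largest at £25,000, the middle of the band.

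**The case against.** The best defence is that the sentence is loose wording. It calls the figures thresholds itself, and the rest of the protocol uses net benefit at those values, so the authors probably meant the probability of being cost-effective at £20,000 and at £30,000. That may be so. But the sentence specifies the number to be reported, and if followed it gives a different number. Clarifying it costs nothing.

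The defence does stand against several stronger readings that a reader might infer:

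- *The PSA summary as a whole would mislead.* The protocol does not call this figure its headline. The preceding sentence plans an acceptability curve, from which the right probabilities can be read, and section 4.2 also plans value-of-information analyses.
- *Strategies would be ranked wrongly.* Nothing ranks them on this probability. They are compared by incremental analysis, and the optimum is set by QALYs and net benefit.
- *The intervention is undefined.* The PICO in section 2.0 defines it broadly, as prophylaxis guided by a risk-assessment tool, against prophylaxis for all or none. What remains is that several tools share that label, so one figure per strategy is needed.
- *The ratio fails because negative QALY differences are likely.* They are possible, since prophylaxis causes bleeding, but nothing shows them to be likely. The primary analysis leaves patients with an identified bleeding risk out of the model. In the first set of inputs above, negative differences occur in only about 0.04% (A) and 0.6% (B, C) of draws.
- *The distortion is about thirtyfold.* That is C over A (0.272/0.009). C over B is about threefold (0.272/0.091). The ratio reflects the inputs chosen.

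**Conclusion.** The point holds for one sentence. As worded, the explicitly reported PSA probability is the wrong statistic: it turns two ceilings into a band, departs from the protocol's own net-benefit criterion, and gives the same low value to clearly good and clearly poor strategies.

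Under the inputs tried, strategies with a mean ICER of £10,000 or less have in-range probabilities from below 0.001 to 0.091, against probabilities of 0.815 to 1.000 of being cost-effective at £20,000. These sizes rest on assumed normal, independent increments and assumed means and spreads. The direction does not: a cost per QALY below £20,000 is outside the band by definition. The acceptability curve, incremental analysis, net-benefit optimisation and value-of-information work are not affected.

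**What to change.** Replace the sentence in section 4.2 with:

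> For each strategy, the probability that it has the highest net monetary benefit among all strategies compared will be reported at £20,000 per QALY and at £30,000 per QALY.

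This agrees with sections 2.0 and 3.1, covers several tools as well as prophylaxis for all and for none, and remains valid if some draws show a QALY loss. An acceptability frontier could be added but is optional. The cost is one edited sentence: the same PSA output is used, with no new data or modelling.
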